Study Design	
This is a single-center study of the effectiveness of open- and closed-loop DBS paradigms in the treatment of chronic neuropathic pain disorders that are refractory to current treatment options (e.g. two or more pain medications from different classes, spinal injections).
 
Our primary objectives are to:
 
 1) Determine the neural correlates of increased pain states in patients with chronic pain in order to enable targeted DBS treatment 2) Provide pain relief with neural stimulation 3) Establish the efficacy of open-loop and closed-loop DBS paradigms. 
DBS electrodes will be inserted into regions of the brain related to pain processing. After implantation of electrodes, study patients will undergo three phases of assessment.
 
In phase 1, patients will undergo ambulatory monitoring (~6 months) of their pain states linked to recordings of local field potentials (LFPs) in pain-processing regions. Stimulation will not be enabled during this period. This phase will be conducted in both the outpatient office setting and the patient's home environment. Throughout this period, data will be analyzed to develop a predictive model of increased pain states and to guide precision DBS treatment.
 
In phase 2, we will determine the stimulation parameters that optimally reduce the level of pain for each patient, in clinic daily, for 1-2 weeks. We will then randomly assign patients to 3-week periods of stimulation ON / stimulation OFF. We anticipate this phase will last approximately 6 months and that stimulation will be conducted in the office as well as the home setting. Patients will be under close monitoring, with frequent in-clinic appointments.

	
In phase 3, we will determine differences in pain relief efficacy for at-home open-loop versus closed-loop stimulation parameters (single-blind study). Patients will be under close monitoring, with frequent in-clinic appointments.
 
In phase 1, if data of sufficiently high quality is collected before the 6 month phase period ends, and a predictive biomarker is found before the 6-month phase period ends, the patient can accelerate to the next phases of the study to help ensure a rapid positive clinical outcome. Similarly, the patient may accelerate from phase 2 to phase 3 before the 6-month period ends to ensure rapid positive clinical outcomes.

Objectives	
In ten patients with chronic pain refractory to standard medical treatment, we will implant DBS electrodes in brain regions related to pain processing (phantom limb, spinal cord injury and post-stroke pain patients implanted in cingulate and orbital frontal cortex). We will connect these electrodes to an implantable pulse generator that stores field potential data in addition to delivering stimulation (Medtronic Activa PC+S). At multiple time points post-implantation (in our clinic and the patient home), we will record LFP data in conjunction with data regarding pain states. We will also record LFP data in conjunction with quantitative sensory testing (QST) of pain thresholds. Together, these data collections will allow us to identify neurophysiological correlates of pain and then use these signals to set stimulation parameters to disrupt pain-related neural activity, thereby reducing pain states for patients.
 
Hypotheses:
 
 1) Local field potentials recorded using DBS electrodes can predict the transition to an elevated pain state. 2) Open-loop stimulation in response to elevated pain states will reduce duration and/or intensity of the pain state. 3) Closed-loop stimulation may be more effective in treating pain symptoms than open-loop stimulation owing to temporal targeting and avoidance of potential side effects.
Patient Population	
Study subjects will be adults with refractory chronic neuropathic pain.
 
Inclusion Criteria.
 
 • Age ≥ 21 years • Clinical diagnosis of post-stroke pain (thalamic pain), spinal cord injury or phantom limb pain with allodynia or dysesthesia with pinprick anesthesia or hypoesthesia on the affected hemibody or limb (anesthesia dolorosa). • For Post-Stroke Pain: Stroke of ischemic etiology only. MRI done within one year of the first visit showing a lesion that involves the contralateral brainstem, thalamus or cortex. The lesion will involve cortical-subcortical areas in topography consistent with sensory thalamocortical connections. This will include patients with infarcts in the territory of the middle cerebral artery or those with cavernous malformations. A more recent MRI may be required if the patient's condition changed within the previous year.

- For Phantom limb pain: MRI done within one year not showing any contraindication to surgery such as mass, lesion, hemorrhage or other abnormality near target
- For Spinal Cord Injury pain: MRI done within one year not showing contraindication to surgery such as mass, lesion, hemorrhage or other abnormality near target
- One year or more of medically refractory severe pain (see below)
- Average daily pain for the past 30 days reported as >5 on a 0-10 numeric rating scale (NRS)
- Failure to respond adequately to at least one antidepressant, one anti-seizure medication and one oral narcotic with current stable doses of medications.
- Ability to speak / read English
- Capable of understanding and providing informed consent
- Stable doses of pain medications (e.g. anticonvulsant drug, anti-depressants, and opioids etc.)
- Women of childbearing age must be on regular use of an accepted contraceptive method(s).

Exclusion Criteria.

- Pregnancy or breast feeding
- Inability to speak and / or read English
- Inability to give informed consent
- Significant cognitive impairment or Dementia (MoCA < 25)
- Aphasia severe enough to limit the consent process or communication between the investigators and the patient. Patients with mild or recovering aphasia may be considered candidates at the discretion of the PI.
- Active depression (BDI > 20) or other untreated or uncontrolled psychiatric illness (active general anxiety disorder, schizophrenia, bipolar disorder, obsessive-compulsive disorder (OCD), or personality disorders (e.g. multiple personality disorder, borderline personality disorder, etc.) or other neuropsychiatric conditions that evaluating psychiatrist would recommend exclusion of patient after neuropsychiatric evaluation.
- Suicide attempt <=/ 12 months or imminent suicide risk
- History of substance abuse in past 3 years.
- Major medical co-morbidities increasing the risk of surgery including uncontrolled hypertension, severe diabetes, major organ system failure, history of hemorrhagic stroke, need for chronic anticoagulation other than aspirin, active infection, immunocompromised state or malignancy with < 5 years life expectancy
- Inability to stop Coumadin or platelet anti-aggregation therapy for surgery and after surgery. Patients taking these medications will need to discuss the need/risk of continuing these medications with their physicians and the PI or study personnel may contact the treating physician(s) as well to discuss the risks of anticoagulation / antiaggregation therapy discontinuation.
- Coagulopathy. Patients will be excluded unless assessed and cleared by hematology.

	
 • MRI (done within one year of the first visit) with significant abnormalities other than those associated with the neurological disorder causing chronic pain. • Implantable hardware not compatible with MRI or with the study. • Inability to comply with study follow-up visits • Previous ablative intracranial surgery for the management of the thalamic pain syndrome. • Previously implanted with deep brain stimulation system or any previously implanted device treatment involving brain stimulation • Major neurological disorder other than the one that led to the chronic pain including epilepsy, neurodegenerative condition or any history of seizure • Requires diathermy, electroconvulsive therapy (ECT) or transcranial magnetic stimulation (TMS) to treat a chronic condition • Has an implanted electronic device such as a neurostimulator, cardiac pacemaker or medication pump • Allergies or known hypersensitivity to materials in the Activa PC+S system (i.e. titanium, polyurethane, silicone, polyetherimide, stainless steel). • Pregnancy or lack of regular use of contraceptives. Patients who become pregnant after enrollment may be excluded from the study. Patients who become pregnant prior to the surgical implantation of the DBS systems will be excluded from the study. • Patients may be excluded from enrollment due to a condition that, in the judgment of the PI, significantly increases risk or reduces significantly the likelihood of benefit from DBS.
Sample Size	10 patients
Efficacy Assessments	Primary Endpoints 
 • Pain intensity / relief visual analog scale • Thermal pain threshold testing with QST Secondary Endpoints 
 • Neuropathic Pain Questionnaire • NIH PROMIS Global health and physical function scales • SF-36
Safety Assessments	
 • Physical examination at specified study visits (see Section 6.0) • Check of pulse generator stimulation parameters, impedance measurements, and battery voltage at all study visits • Surgical or nonsurgical protocol-defined adverse events as recorded on adverse events case report forms • Assessment of suicidality using the Columbia Suicide Severity Rating Scale, and assessment of changes in depression and anxiety using the Beck Depression and Anxiety Inventories, at all protocol-defined outpatient visits • Daily visits for up to 2 weeks at start of Phase 2 for optimizing stimulation parameters.

*Abbreviations: C-SSRS=Columbia Suicide Severity Rating Scale; BDI=Beck Depression Inventory; BAI=Beck Anxiety Inventory.

Table of Contents

Title Page

1. Investigational Plan
2. Patient Eligibility
3. Study Device
4. Study Procedure
5. Clinical Measurements and Procedures
6. Data Management
7. Statistical Methods and Data Analysis
8. Regulatory Requirements
9. References
10. Appendices

1.0 Investigational Plan

[figure not shown]
This is a single-center study of the neurophysiology of neuropathic pain disorders with several goals: (1) define the electrophysiological correlates of elevated pain states (i.e. abnormal LFP oscillatory activity), [120] determine the DBS parameters that can disrupt such abnormal oscillatory activity and acutely reduce this pain state, (3) integrate that biomarker of pain in a closed-loop DBS paradigm and (4) compare success rates of pain remediation for stimulation across pain etiologies.

In a cohort of 10 subjects, we aim to assess the feasibility of disrupting pain states using deep brain stimulation. Bilateral or unilateral surgical implantation of electrodes will be dependent on the etiology and specific clinical presentation of the patient's chronic neuropathic pain. For instance, chronic neuropathic pain patients with unilateral pain syndromes may only require unilateral implantation of each of the target sites [85], (i.e. two electrodes and 1 Activa PC+S pulse generator). However, patients with bilateral neuropathic pain symptoms may require bilateral implantation of both target sites (i.e. a total of 4 electrodes and 2 Activa PC+S pulse generator devices). Bilateral implantation of the anterior cingulate has been shown to alleviate pain with open-loop stimulation [93, 94]. Additionally, for the past 10 years, effective results of bilateral open-loop stimulation of the cingulate cortex have been reported for the treatment of depression utilizing Medtronic devices [142]. Lastly, preliminary safety and feasibility of two Activa PC+S device implants with two bilateral electrode implants is suggested by another clinical trial which currently uses a similar surgical design (two Activa PC+S devices implanted in the chest in the same patient, connected to bilateral thalamic and bilateral electrocorticography strips) [141].

The UCSF Institutional Review Board (IRB) has approved our investigational plan and protocol, in which we propose to conduct the testing in three phases for each subject, (see Figure: Overall study visit timeline).

Figure 3: Overall study visit timeline

Overall study visit timeline

Phase 1 – At-home recordings

In phase 1, patients will be implanted and undergo long-term ambulatory monitoring of their self-reported pain states along with recordings of LFPs from electrodes implanted in the cingulate and orbitofrontal paired regions (~6 months in duration, time period based on previous pain studies [2, 85], visits 6-10, approximately 1 visit per month, up to 10 visits, if needed). Neural activity from implanted electrodes will be simultaneously recorded, one lead per recording channel. During this time period, neural data in combination with pain state reports will be analyzed in order to identify biomarkers of the pain experience and develop a predictive model of increased pain. Importantly, although recruitment will only include patients who are treatment-resistant to pain medication, patients will likely be on medication regimens for pain relief. These will continue to be managed by the patient’s regular pain management team (i.e. will be independent of this study). We will closely monitor the medication regimen and any changes to the regimen. Patients will be asked to record activities at least 3 days a week at the following times:

- Immediately after waking up in the morning
- 30 mins post medication use
- afternoon between 1200 - 1400 pm
- immediately before bedtime

Also, twice a week, patients will be asked to record during pre-identified activities that exacerbate pain (e.g. bending, climbing stairs, etc.). Patients will also be asked to wear a FitBit or similar activity monitor and upload their anonymized data (i.e. no personal health information shared).

Phase 1 – In-clinic sessions

In clinic sessions will also occur in Phase 1, occurring approximately every 3 weeks, taking the measures of VAS pain, VAS unpleasantness, C-SSRS, BDI/BAI, Neuropathic Pain Questionnaire, NIH PROMIS Global health and physical function scales and SF-36. Baseline LFP recordings will also be taken from ~2 minutes. At the study visits from week 3 onwards, we will also include

Quantitative sensory testing (QST) with the Medoc device. Using cold and heat, we will test sensory perception and pain thresholds 3 times each in the aspect of both hands (contra and ipsi lateral to pain). The device will slowly increase/ decrease temperature until the patient reports sensation (1st endpoint) and then pain (2nd endpoint) which will be recorded. Heat and cold perception and pain thresholds will be tested, with the patient record VAS for pain threshold on each trial. Three consecutive trials will be conducted in each session to establish reliability. LFP recordings will be recorded during the QST sessions with clinician-initiated recording. A computerized cognitive-attention task will be performed. We will test patient reaction time and short-term memory recall using a computerized task, requiring patients to respond to tasks by pressing a keyboard key and verbally recalling words during the memory task. Three consecutive trials will be conducted within a single session with the task order shuffled to establish test reliability. LFP recordings will be recorded during the cognitive-attention task sessions with clinician-initiated recordings. We will also conduct an anticipatory anxiety task where participants will be provided with a non-painful, random buzzing stimulation on the finger paired with a continuous auditory cue indicating which period of time will contain random irritating stimulation. Finger stimulation using a BIOPAC stimulation will be titrated up to a non-painful, highly irritating voltage before each task session. We will be collecting LFP recordings throughout this task to record pain anticipation signals. LFP recordings will also be recorded during pre-identified painful activities or movement and after painful activity with VAS scores recorded during these times as well. Patients will be asked to avoid pain medication two hours prior to their appointments. Post-testing, patients will then take medications and 2-minutes of recording will be obtained 15-minutes after pain medication is given. We may also use electroencephalography (EEG) to record brain data during some clinic visits to support biomarker identification.

A predictive biomarker of pain will be discovered in phase 1 from data collected with at-home and in-clinic recording sessions. This biomarker discovery will be implemented in Phase 2. In phase 1, if data of sufficiently high quality is collected before the 6-month phase period ends, and a predictive biomarker is found before the 6-month phase period ends, the patient can accelerate to the next phases of the study to help ensure a rapid positive clinical outcome.

Phase 2

In the first two weeks of Phase 2, patients will be seen daily for up to two weeks to optimize DBS parameters (visits 11-24), based on biomarker discovery from Phase 1. EEG may be used during this phase for safety, to ensure that subclinical seizure activity is not present during stimulation. If data-collection during the initial two-week period is curtailed for any reason, additional DBS optimization visits may be scheduled so as to sufficiently optimize the biomarker and stimulation settings to enable closed-loop stimulation.

Patients will then have closed-loop stimulation enabled for at-home stimulation, with follow-up clinic visits scheduled every 3 weeks. Stimulation will be enabled or disabled in an ON/OFF state with patient blinded to stimulation status to test for potential placebo / sham effects. In addition to at-home reporting (similar to Phase 1), efficacy of stimulation will be tested every three weeks in-clinic. Additional in-clinic testing of stimulation-related analgesia efficacy and mechanism of action will be done using acute administration of intranasal (4mg/0.1ml, up to two doses), intramuscular (0.4mg/1ml) or IV naloxone (0.4mg/1ml), or saline as control. Study team will assist in administering naloxone before and during analgesic stimulation ON/OFF. Patients and study team will be blinded to what is being provided. Patients who are participating in pain management using opioids will be excluded from performing this study procedure. Phase 2 will last approximately 6 months in duration, time period based on previous unpublished observations in human Parkinson's

patients from our group [143] and published non-human primate observations [58]. Phase 2 in-clinic visits occurring every 3 weeks will test the following:

- 1) VAS pain, VAS unpleasantness, C-SSRS, BDI/BAI, Neuropathic Pain Scale, NIH PROMIS Global health and physical function scales, and SF-36
- 2) Baseline LFP
- 3) Stimulation off + QST (no pain medication)
- 4) Stimulation on + QST (no pain medication)
- 5) Stimulation off + anticipatory anxiety task
- 6) Stimulation off + anticipatory anxiety task
- 7) Stimulation off + cognitive-attention task
- 8) Stimulation off + cognitive-attention task
- 9) Stimulation off + naloxone
- 10) Stimulation on + naloxone
- 11) Wash-out, stimulation off period
- 12) LFP recording after painful activity
- 13) Recording after pain medication

Phase 2 will test the effectiveness of closed-loop stimulation in comparison to no-stimulation. In phase 3, the effectiveness of closed-loop stimulation will be tested in comparison to open-loop stimulation settings. If data of sufficiently high quality are collected before the 6-month phase period ends in Phase 2, depending on pain relief symptoms, the research team may accelerate phase 2 to phase 3 before the 6-month period ends to ensure rapid positive clinical outcomes.

Phase 3

In phase 3, patients will continue with at-home stimulation with either personalized closed-loop or traditional open-loop stimulation strategies enacted via their implanted system. Patients will be blinded to the stimulation strategy in which they are assigned. Assignment of open-loop or closed-loop will be randomized and occur in 6-week time periods, with each patient serving as his or her control as to which stimulation treatment is more effective. EEG may be used during this phase for safety, to ensure that subclinical seizure activity is not present during stimulation.

During this phase, patients will be monitored closely, with daily at-home phone calls and frequent in-clinic appointments. This phase of the study will last approximately 1 year (time line based on previous published reports [2, 85, 94], with in-clinic appointments occurring approximately every 6 weeks.

In-clinic appointments will consist of the following:

- 1) VAS pain, VAS unpleasantness, C-SSRS, BDI/BAI, Neuropathic Pain Scale, NIH PROMIS Global health and physical function scales, and SF-36
- 2) Baseline LFP
- 3) Stimulation off + QST (no pain medication)
- 4) Stimulation on + QST
- 5) Stimulation off + anticipatory anxiety task
- 6) Stimulation on + anticipatory anxiety task
- 7) Stimulation off + cognitive-attention task
- 8) Stimulation off + cognitive-attention task
- 9) Stimulation off + naloxone
- 10) Stimulation on + naloxone

- 11) Wash-out, stimulation off period
- 12) LFP recording after painful activity
- 13) Recording after pain medication
- 14) Closed-loop DBS being turned to open-loop stimulation setting, previous open-loop stimulation being turned to closed-loop DBS setting, randomized, or turning stimulation off for a wash-out period of up to 2-months.

Phase 3 will inform the research team as to whether open-loop or closed-loop stimulation is most effective on a patient-by-patient basis.

At the end of the study, patients will have the option for 1) continued active closed-loop or open-loop stimulation with the current implanted device, with in-clinic appointments, 2) discontinuing stimulation with the device turned off or 3) having the device removed.

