3.0 Study Procedure

Study Duration: The duration of this pilot study will be five years. We expect that all 10 patients will be recruited in the first 2.5 years, and data collection, stimulation and analysis will be completed at 5 years.

Patient recruitment and clinical characterization: Patients with refractory chronic neuropathic pain specific to spinal cord injury, post-stroke or phantom limb pain will be recruited from clinics specializing in chronic pain at UCSF and the San Francisco VA Medical Center. To the extent possible within our patient population, we will seek to minimize the diversity of neuropathic pain diagnoses represented across the two pain etiologies thereby optimizing opportunity for cross-patient comparative analysis.

The overall study design is summarized in **Figure 3: Overall study visit timeline. Also see Table: Protocol chart.**

The schedule of events is as follows:

PHASE 1:

Prior to surgery

1. Prior to the start of the study, an informal phone interview to schedule in-clinic evaluation will take place, **(noted as visit 1.1)**. An in-person visit at the clinic will then be scheduled.

2. The research study PI(s) will obtain informed consent at the in-person visit at the clinic. During this visit, **(noted as visit 1.2)** the study team will begin establishing eligibility based on the following inclusion and exclusion criteria, **with method for establishing eligibility in parenthesis.**

i. During this visit, PI will obtain consent for medical record review by HIPAA authorization form signed by patient. Medical record review will be also done after the in-person visit.

ii. Pregnancy test and other paper-pen testing as noted below will also be conducted.

This visit will primarily serve to obtain consent for the study and HIPAA authorization, as well as discuss the study in detail and answer any questions and begin confirmation of inclusion/exclusion criteria of the patient.

iii. During visit 1.2, Inclusion / Exclusion criteria will be investigated as follows:

Inclusion:

- Patient is age ≥ 21 years **(medical record review and asking patient);**
- Clinical diagnosis of post-stroke pain (thalamic pain), Spinal Cord Injury or phantom limb pain with allodynia or dysesthesia with pinprick anesthesia or hypoesthesia on the affected hemibody or limb (anesthesia dolorosa), **(medical record review);**

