6.0 Statistical Methods and Data Analysis

Ratings of pain will be measured by visual analog scales for pain as well as unpleasantness of pain sensation (i.e. “how much pain are you in right now?” and “how much is the pain bothering you right now?”). Patient reports of sensory and pain detection using the Quantitative sensory testing (QST) with the Medoc device will also be used, with and without stimulation.

In Phase 2, patients will serve as their own controls in a single-blinded phase (6-months in duration) in which placebo versus active open-loop stimulation is used. During this 6-month period, four sham and four active stimulation periods will occur in a random, blinded assignment. During the 8 in-clinic visits, the threshold for sensory and pain detection with the Medoc device will be used and scores will be compared for each patient during sham versus active stimulation periods in one-sample, two-tailed t-test. The 10 patients’ sham versus stimulation scores will also be used in group analysis to test the effects of open-loop and closed-loop stimulation.

In Phase 2, the visual analog scale scores recorded during the at-home recording sessions for various activities will be compared for each patient [(see Figure 3; 168 scores for sham sessions and 168 scores for active stimulation sessions, per patient); (i.e. 3 times per week for 4 activities and 2 times per week for at least 1 painful activity, for at least 14 VAS scores per week; 24 weeks total with 3 weeks per session-sham or stimulation, 8 sessions total, 4 sham sessions and 4 stimulation sessions)].

Multiple regression analysis of all patients will also be used to test for effects of stimulation on various activities, time of day, stimulation effects over time in trial and potential differences in stimulation effects on pain etiologies (i.e. spinal cord injury versus phantom limb versus post-stroke).

Phase 1 (no-intervention) VAS scores will be compared to Phase 2 (sham controlled and active stimulation) VAS scores.

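### The regression test of etiology differences has only 10 patients behind it: pooling repeated scores can inflate false positives, a patient-level test has little power, and goal 4 is best reported descriptively

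*Combined protocol and SAP*

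**What the plan says.** Section 1.0 lists four goals. The fourth is to "compare success rates of pain remediation for stimulation across pain etiologies". The setting is small and is described as a feasibility study: "In a cohort of 10 subjects, we aim to assess the feasibility of disrupting pain states using deep brain stimulation".

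Section 6.0 gives the matching analysis, once for Phase 2 and once for Phase 3. It is a multiple regression of all patients which, among other effects, tests for "potential differences in stimulation effects on pain etiologies (i.e. spinal cord injury versus phantom limb versus post-stroke"). The outcome is the score, not a success rate. No patient term, error structure or laterality term is given. The sample size paragraph says there is no formal calculation, and it counts the at-home sessions as a source of added statistical power.

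Two other places bear on the comparison. On surgery, section 1.0 says "Bilateral or unilateral surgical implantation of electrodes will be dependent on the etiology and specific clinical presentation of the patient's chronic neuropathic pain". On recruitment, section 3.0 says "we will seek to minimize the diversity of neuropathic pain diagnoses represented across the two pain etiologies", "thereby optimizing opportunity for cross-patient comparative analysis". That sentence counts two etiologies. The eligibility criteria, the first part of the same recruitment paragraph and section 6.0 all name three.

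**The concern.** A patient has one etiology throughout. However many scores each patient supplies, the etiology contrast rests on 10 independent units, or three to four per group if they are spread evenly. No quota or minimum per etiology is set. Repeated scores sharpen each patient's own ON-OFF difference but say nothing new about how patients with the same etiology differ from one another.

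A regression that treats all scores as independent judges etiology against the wrong variation. A group of three or four patients who respond differently by chance, or whose stimulation periods fall in good or bad weeks, can then appear as an etiology effect. At stake is whether a reported etiology difference, or its absence, means anything.

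Two matters of definition add to this. Goal 4 speaks of success rates, but no success criterion is set for a patient; the end of section 6.0 describes benefit only for the study as a whole. The number of groups to be compared is also stated inconsistently.

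**Working it through.** **Inputs from the documents.** N = 10; three etiologies; Phase 2 has four sham and four active periods per patient. Scores per week: 3 × 4 + 2 × 1 = 14. Over 12 weeks per condition this is 14 × 12 = 168, which reproduces the plan's figure. Per patient: 168 + 168 = 336 in Phase 2, and about 364 + 364 = 728 in Phase 3.

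**Inputs assumed.** Two-sided 5% level; 4/3/3 split; residual SD 2; period SD τ from 0 to 1; SD ω of the true ON-OFF effect between patients from 0 to 1; patient intercepts in the model. The documents give none of these.

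**1. Pooled-score test of stimulation by etiology, no true etiology difference.**

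Actual variance of one patient's ON-OFF difference: V = 2·2²/168 + 2τ²/4 + ω².

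Variance used if scores are taken as independent: V₀ ≈ 2·(2² + τ² + ω²/4)/168.

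The test statistic is inflated by R = V/V₀. With three groups and many residual df, it behaves as R times a chi-square on 2 df, so the rejection rate is about 0.05^(1/R).

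| τ | ω | V | V₀ | R | Approximate rejection rate |
|---|---|---|---|---|---|
| 0 | 0 | 0.048 | 0.048 | 1.0 | 5% |
| 0.25 | 0 | 0.079 | 0.048 | 1.6 | 16% |
| 0.5 | 0 | 0.173 | 0.051 | 3.4 | 42% |
| 0.5 | 0.5 | 0.423 | 0.051 | 8.2 | 70% |
| 1 | 0.5 | 0.798 | 0.060 | 13.2 | 80% |
| 0.5 | 1 | 1.173 | 0.054 | 21.9 | 87% |
| 1 | 1 | 1.548 | 0.063 | 24.8 | 89% |

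Simulation of the same model agrees: 5% with both SDs zero, about 16% and 43% in the next two rows, and 69% to 89% over the last four.

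**2. Patient-level test.** Each patient contributes one ON-OFF difference, compared across etiologies with 10 − 3 = 7 df. Simulated rejection under the null is 4% to 6% in all these settings. For power, the noncentrality of a pairwise t-test is d·√(n₁n₂/(n₁+n₂)), where d is the difference in between-patient SDs. With 7 df, 80% power needs a noncentrality of about 3.27:

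- 3 v 3: d = 3.27/√1.5 = 2.67; power at d = 1 is 19%.
- 4 v 3: d = 3.27/√(12/7) = 2.50; power at d = 1 is 21%.

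**3. If success were made binary.** Complete separation gives Fisher p = 0.10 for 3 v 3 and p = 0.029 for 4 v 3. The exact 95% interval for 2 successes in 3 patients is 9% to 99%. A three-group exact test with a 3/3/4 split has 26% power at assumed rates of 20/50/80%, and 76% at 10/10/90%.

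**4. Laterality.** Three etiologies by two implant types make six cells, and 10/6 ≈ 1.7 patients per cell.

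**The case against.** This is a declared pilot without a sample size calculation. Etiology appears in none of the three primary objectives, the hypotheses or the criteria for going on to a larger trial. Section 6.0 speaks only of potential differences, which is exploratory language. Low power for a subsidiary goal is inherent at this size, and a descriptive comparison remains possible. All of that stands. It is a reason to label goal 4 accordingly, not to keep a test with the wrong error term.

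Section 6.0 also allows general linear mixed models because the sample is small. That option sits in the paragraph on field potentials and commits to nothing for the etiology regression. The plan does not state that regression's error structure, so the inflation is conditional: it applies if scores are treated as independent, and it vanishes if neither period effects nor patient differences exist.

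A reader might infer more than the documents support:

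- **That recruiting to limit diversity defeats the comparison.** The stated purpose is to help cross-patient comparison, and the sentence can mean more uniform diagnoses within etiologies.
- **That etiology and laterality cannot be separated.** Laterality depends on clinical presentation as well, and the examples in section 1.0 turn on unilateral or bilateral pain. It may vary within an etiology.
- **That an etiology result would decide who enters a later trial.** No criterion in section 6.0 uses it.
- **That no result could ever be significant.** This is true of a 3 v 3 Fisher test but not of 4 v 3.

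**Conclusion.** The concern holds for inference about etiology. With 10 patients, the planned regression has two possible outcomes. If pooled scores are treated as independent, the false-positive rate runs from about 16% to 89% over the non-zero SD settings examined. If patients are the unit, the error rate is right, but only differences of about 2.5 to 2.7 between-patient SDs are detectable with 80% power.

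The size of the inflation rests on assumed SDs; its direction follows from the design. The power figures rest on a 4/3/3 split. Confounding with laterality is a risk arising from sparse cells, not an established feature of the design. The missing patient-level definition of success and the mismatch between two and three etiologies stand on the text alone.

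**What to change.** - In section 1.0, state goal 4 as exploratory and descriptive. Replace success rates with the patient-level differences actually analysed, since no success criterion per patient exists.
- List each patient's ON-OFF and open-closed differences beside etiology and unilateral or bilateral implant.
- In both etiology regressions in section 6.0, remove the etiology test from the pooled model, or test it only against between-patient variation (7 df with three etiologies).
- In section 3.0, reconcile the count of two etiologies with the three named elsewhere.

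These are wording changes and need no new patients or data. The cost is that the trial gives up an inferential claim about etiology.
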